5.7 Withdrawal of Subjects

If the study subject becomes a threat to the safety of others in his or her treatment group, or to the research team, that subject's participation in the study will be terminated, and they will be withdrawn from the research without their consent.

If a study subject demonstrates behavior that repeatedly violates the community guidelines of their treatment group, so much so that they actively prevent the group from being able to achieve the day's curriculum or they create a hostile environment for other group members or research staff, that subject's participation in the groups will be terminated, and the PIs will determine if they can continue to participate in the study and complete the research assessments with study staff.

If a subject wishes to withdraw from the study before all procedures are complete, he or she simply needs to notify the study's project manager, study coordinator, or other study team member by phone or in person that he or she no longer wishes to participate, and the subject will be withdrawn from the study and no longer contacted regarding study procedures. A primary study contact number will be provided to each participant, so they know how to reach the study team to request early withdrawal (or for any other questions).

6.0 Reporting

Safety Monitor: [name], a clinical psychologist based at the Seattle division of VA Puget Sound, will serve as the unbiased safety monitor for the study. [name] has extensive experience in clinical psychology. She is outside of the key study investigators and she will review any adverse or unanticipated events and provide an unbiased written report to the PI's within 10 calendar days. She will assess whether there is a relationship between the adverse or unanticipated event and the study procedures, and will indicate whether they concur with the details of the report provided by the PI's. Any events deemed by the safety monitor team or the PI's to be possibly related to the study procedures will be promptly forwarded to the VA Puget Sound IRB Office of Risk Management.

When an unexpected serious adverse event occurs, we will log it in an "Adverse Events & Problems" log, to be used for providing reports to the Data Safety Monitor, in addition to submitting a report to the IRB within 5 days as required. All other adverse events, problems, and protocol deviations will be logged and reported to the Data Safety Monitor and the IRB with annual reviews.

At the midpoint of the study, the data monitor would then analyze whether significantly greater adverse events occur in one arm of the study, which might warrant stopping the study.

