Human Subjects Protocol

VA Puget Sound IRB

An Evaluation of MBSR and CBT for Veterans with Chronic Pain

Lay Title: Investigating Methods of Pain Recover with Qutpatient Veteran Education
("IMPROVE")

Funding Agency: VA Office of Rehabilitation Research and Development

Principal Investigator: [name]

MIRB 01889

Version 8; 8/11/2023

Abstract

Pain is one of the most common reasons Veterans seek health care. Mental health conditions (including PTSD, anxiety, and depression) are estimated to co-occur for 30-50% of Veterans with chronic pain. Mindfulness-Based Stress Reduction (MBSR) and Cognitive Behavioral Therapy for chronic pain (CBT-CP) teach skills intended to enhance functionality and quality of life in the face of chronic pain. The study will recruit and randomize up to 222 Veterans with chronic musculoskeletal pain. One third of these (n=74) will be randomly assigned to the Mindfulness-Based Stress Reduction (MBSR) group, one third of these (n=74) will be randomly assigned to the Cognitive Behavioral Therapy for Chronic Pain (CBT-CP) group, and one third of these will be assigned to Treatment as Usual (TAU). The MBSR and CBT-CP sessions meet by video once a week for 8-weeks, MBSR sessions are 2 hours long per session, and CBT-CP sessions are 1.5 hours long. The **Primary Aim** is to assess if MBSR and CBT-CP each result in greater reductions in the pain interference subscale of the Brief Pain Inventory (BPI) as compared to usual care, from baseline to 6 months post-treatment. The **Secondary Aim** is to evaluate if MBSR and CBT-CP are each superior to usual care in producing improvements in pain severity, treatment satisfaction, and depression.

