5.0 Study Procedures

5.1 Study Design

The proposed study is a three-arm comparative effectiveness trial that will randomly assign Veterans with chronic musculoskeletal pain to MBSR, CBT for chronic pain (CBT-CP) or usual care to assess the effectiveness of MBSR or CBT-CP for Veterans with chronic musculoskeletal pain. Veterans with chronic

musculoskeletal pain (N =222) will be randomized to either 8 weeks of MBSR (n =74), 8 weeks of CBT-CP (n =74) or usual care (n=74), and will complete assessments at baseline, immediately post-treatment and at 6-month post-treatment. Randomization will be performed through REDCap, and stratified by sex assigned at birth and pain severity score. Sessions will be audio recorded using both Philips DPM 8000 recorders and OBS Studio software. Fidelity coding from audio recordings will evaluate protocol adherence for both MBSR and CBT-CP.

A comprehensive outline of the various data collection tools/measured to be administered at each of the three assessments is provided in **Section 5.5 Study Evaluations**.

Risk and Benefit: The risks for this study involve the potential for psychological distress associated with collection of self-report data, and the possibility that undergoing either the MBSR class or CBT-CP could be stressful and worsen symptoms. There is also a risk of confidentiality due to the group nature of MBSR and of CBT-CP, and the delivery of these groups by the VVC internet based platform; those who are unwilling to be in an MBSR class or CBT-CP group that is being audiotaped will need to seek other services. Further, there is a risk that MBSR and CBT-CP will not be efficacious for some individuals. We plan to educate patients about the possible risks and benefits prior to study enrollment by providing a thorough orientation to the research and an overview of each intervention prior to giving informed consent. Potential benefits for those randomized to either condition may take the form of reduced chronic musculoskeletal pain symptoms, and increased health-related quality of life. Veterans' families may also benefit as a result of the shift in emotional state. However, a participant may not benefit directly from participation in the study. Information gained in the study may be of benefit in the future to persons with chronic musculoskeletal pain. Specific measures for minimizing risk are outlined below.

Procedures to Minimize Risk to Subjects and Protect Confidentiality:

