- 5) If some participants experience unexpected levels of distress following participation in the research, we will take the following steps to minimize this possibility: We will state clearly in the consent forms that participation in the research study may involve discussing details about traumatic events and about symptoms. In addition, at the beginning and end of each of the assessment sessions, we will provide participants with time to ask questions. We will inform participants, both prior to the initial screening questions on the phone and prior to beginning treatment, that some individuals do experience increases in symptoms after discussing aspects of the traumatic experience and that if these symptoms do not return to their prior levels within a few days, participants are encouraged to call the Investigative Team. We will provide all participants with a study phone number they can use to alert us if they are experiencing distress. The phones will be checked daily for messages and distressed participants will be called the same day (for calls made during business hours or the next business day for after hour calls).
- 6) If any point in the study during the assessments or treatment sessions a participant endorses suicidality or homicidality, the group instructor(s) will notify the PI ([name]), or [name], who will contact the patient. Drs. [name] and [name] are licensed Clinical Psychologists with extensive experience in assessment and treatment of Veterans. Should there be concern

about risk of harm, a clinical interview will be conducted to assess level of risk and need for intervention. Participants who indicate acute suicidality or homicidality including a plan will be immediately referred for VA mental health services. It is important to note that in more than 7 years of conducting clinical research, we have never had a participant unwilling to accept referral for suicidality and have never had to make an involuntary admission or report.

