OME Opioid Use Tracking	B, P, 6		Opioid Use
VA mental health care			
VINCI data pull			Opioid use, prescription sleep medication use, other care (visits for pain, pain-related procedures), markers of suicidality (high-risk suicide flag, psychiatric admissions, deaths due to suicide)
CPRS review for engagement in other treatments	8-months post-baseline	dichotomous	Other care received during study

Full text of measures in appendix.

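### The midpoint adverse event comparison may partly measure contact: the active arms have eight weekly sessions at which events can be noticed, and the supplied text has no enquiry common to all arms

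*Combined protocol and SAP*

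**What the plan says.** Section 6.0 gives the monitor a between-arm task: "At the midpoint of the study, the data monitor would then analyze whether significantly greater adverse events occur in one arm of the study", with the consequence "which might warrant stopping the study". It names no test, significance level, event definition, denominator or date for the midpoint. On collection, the same section says: "All other adverse events, problems, and protocol deviations will be logged and reported to the Data Safety Monitor and the IRB with annual reviews". Unexpected serious events are logged and reported sooner.

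Contact differs by arm. The Abstract says: "The MBSR and CBT-CP sessions meet by video once a week for 8-weeks". Usual care has no sessions. Section 5.1 says that participants in all three arms "will complete assessments at baseline, immediately post-treatment and at 6-month post-treatment".

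Section 5.1 also describes how events reach the team. If "during the assessments or treatment sessions a participant endorses suicidality or homicidality, the group instructor(s) will notify the PI", follow-up begins; so sessions are a detection route, alongside assessments. For everyone, "We will provide all participants with a study phone number they can use to alert us if they are experiencing distress".

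The table in Section 5.5 lists scales, interviews and record reviews. It includes a VINCI pull covering "markers of suicidality (high-risk suicide flag, psychiatric admissions, deaths due to suicide", with no stated timing and no link to the midpoint comparison. It lists no adverse event enquiry at the post-treatment or 6-month visit.

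**The concern.** A comparison of adverse event counts is interpretable only if an event has about the same chance of being recorded in each arm. Here a participant in MBSR or CBT-CP meets study staff weekly for eight weeks, and a usual care participant does not. An episode of distress or worsening that passes within a few weeks may be heard in a session in one arm and never be recorded in the other.

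The comparison can lead to stopping, so the direction of the error matters. Over-recording in an active arm would exaggerate its apparent harm. It could also hide a true benefit of the active arm, or harm occurring in usual care. Section 5.1 names worsening of symptoms as a possible effect of either intervention, so an observed excess might be partly real. With unequal detection, the monitor could not tell the two apart. MBSR against CBT-CP is largely unaffected, since both have the same number of weekly sessions.

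**Working it through.** **Arm size.** The plan gives no figure for the adverse event comparison, only the arm sizes. These reproduce: a two-sample t-test with d = 1.05/2.1 = 0.50, 80% power and two-sided 5% needs 63.8, so 64 per arm; 64 × 1.15 = 73.6, so 74 per arm and 222 in total. Half of 74 is 37. Taking the midpoint as half of enrolment is an assumption.

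**Contacts after baseline.** Active arm: 8 sessions + 2 assessments = 10. Usual care: 2.

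**Test.** Assumed: two-sided Fisher exact test at 5%, one active arm against usual care, 37 v 37, with exact enumeration of both binomials. True risk is equal throughout, so every significant result is false. Nearly all such results point against the active arm.

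**(a) Every contact equally likely to surface an event.** Recorded proportion = 1 − (1 − q)^k, with k = 10 or 2.

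| q per contact | Active | Usual care | False significance |
|---|---|---|---|
| 0.5% | 4.9% | 1.0% | 0.6% |
| 1% | 9.6% | 2.0% | 7.4% |
| 2% | 18.3% | 4.0% | 34.5% |
| 3% | 26.3% | 5.9% | 58.4% |

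If only the two shared contacts count in both arms, the same test is falsely significant in at most 0.5% of trials in each row.

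**(b) Calls surface more than sessions.** Active = 1 − (1 − s)^8 (1 − c)^2; usual care = 1 − (1 − c)^2.

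| s per session | c per call | Active | Usual care | False significance |
|---|---|---|---|---|
| 1% | 5% | 16.7% | 9.8% | 7.6% |
| 1% | 10% | 25.3% | 19.0% | 6.0% |
| 2% | 10% | 31.1% | 19.0% | 16% |

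**(c) Fixed true rate, different fraction captured.** Recorded proportion = true rate × fraction captured.

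| True rate | Captured (active v usual care) | Recorded | False significance |
|---|---|---|---|
| 30% | 80% v 40% | 24% v 12% | 18.6% |
| 20% | 80% v 40% | 16% v 8% | 9.7% |
| 10% | 80% v 40% | 8% v 4% | 1.9% |
| 5% | 80% v 40% | 4% v 2% | 0.2% |
| 30% | 80% v 60% | 24% v 18% | 5.8% |

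**(d) A different test and model.** Suppose a fraction r of participants has an event, each contact records an existing event with probability q, and a pooled z test is used. With r = 30% and q = 0.2, usual care records 0.3 × (1 − 0.8^2) = 10.8% and an active arm 0.3 × (1 − 0.8^10) = 26.8%; a false excess against the active arm is significant in 43% of trials. Over r = 10% to 50% and q = 0.1 to 0.5, the chance runs from 6% to 71%.

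The direction is the same in every model. The size depends almost wholly on rates that the documents do not give.

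**The case against.** Several points on the other side stand.

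- **Usual care is not unobserved.** All participants have the phone line, messages are checked daily, and participants are encouraged to call if symptoms do not settle. Suicidality endorsed at an assessment is escalated, and depression, PTSD symptoms and pain are measured on the same schedule in every arm. These routes narrow the gap. They do not close it: the line depends on the participant calling, and the scales are listed as outcomes, not as adverse event triggers.
- **A group session need not yield as much as an individual interview.** Each call also looks back over a longer period. This is fair, and table (b) shows it shrinks the problem. If calls recovered everything since the last contact, the extra sessions would add nothing.
- **Serious events could be found in records for all arms.** Hence the concern bears mainly on distress, worsening and voiced suicidality.
- **The evidence on collection is partial.** The full text of the measures is in an appendix that was not supplied, and some pages were removed. That events are logged only as they come to notice is an inference.

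Three stronger readings are tempting, and the documents do not support them. A reader might infer a formal stopping rule that would halt the trial; Section 6.0 says only that a difference might justify stopping, and the monitor also reviews events for relation to study procedures. That review softens the problem but cannot recover usual care events that were never recorded. A reader might infer that counts are bound to differ; the text supports only that they may. A reader might also infer that true harm in an active arm could be masked; over-recording there works the other way.

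**Conclusion.** The point holds as a low-cost improvement to the safety comparison. Section 6.0 calls for a between-arm significance comparison, sessions are a detection route that usual care lacks, and nothing in the supplied text equalises detection. Followed as written, the comparison can show an excess in an active arm that reflects contact alone.

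In the Fisher scenarios, the chance of a false significant difference runs from below 1% to about 58%. The low end applies when events are rare, and the chance falls towards the test's own error rate as the shared routes capture nearly everything. The high end needs 3% detection at each of 10 contacts against 2. Neither end is a bound: a pooled z test under another detection model reached 71%. All figures rest on assumed rates, equal true risk, 37 per arm and a test that the protocol does not name. They show that the bias could matter, not how large it will be. The efficacy analysis is not touched by this point.

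**What to change.** 1. Add one adverse event question, worded identically and with the same look-back period, to the post-treatment and 6-month calls in all three arms, and list it in the Section 5.5 table.
2. In Section 6.0, make the primary midpoint between-arm comparison the events found by that question, plus record-based events (psychiatric admissions, high-risk flags, deaths) where VINCI data are available by then.
3. Beside it, show the count of all logged events by arm, with the source of each marked: session, call, phone line or records. The monitor then still sees any session-related harm and can judge how far an excess comes from sessions.
4. Keep individual review of every event noticed in a session exactly as now.

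The cost is one interview item and some rewording. The primary comparison will rest on fewer events, so it loses some sensitivity to harm voiced only in sessions; the all-events display is there for that reason. Using records at the midpoint may need an earlier VINCI pull, since Section 5.5 gives that pull no date and puts the CPRS review at 8 months after baseline.

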7.0 Privacy and Confidentiality

The study will obtain Protected Health Information by collecting data (e.g. medications and other treatment relevant to the symptoms evaluated for the study) from the subjects' CPRS records, as well as contact information (PII) for following up with subjects regarding ongoing study procedures. Health information will also be collected through the questionnaires and interviews. This health information will be maintained as de-identified study data and will not be disclosed to unauthorized entities. We will be obtaining a Certificate of Confidentiality for this study, as we ask about substance use.

Because we are using VVC for group delivery, and internet based platform, we will warn participants of potential risks to confidentiality of this delivery method, do visual confirmations of group participants, and lock group rooms to prevent intrusions.

A password-protected crosswalk will be maintained to link identifying information (full names and last 4 SSN) to study subjects' unique study IDs (e.g. 695-001, 695-002, 695-003....695-308). All files containing study data, hard copy or electronic, will include only the subject's study ID so that no data can be linked directly to an individual. All study team members, as VA employees (WOC or otherwise) are required to undergo Privacy & HIPAA training as well as VA Privacy and Information Security Awareness and Rules of Behavior. Any non-VA-affiliated study team members will be required to undergo equivalent training. Only study team members will have access to the electronic study folder, located on the R: drive on the VA server. Hard copy data and consent forms will be stored in locked filing cabinets in the offices of the PI and/or the Project Manager.

8.0 Communication Plan

N/A, this is not a multi-site research project.

9.0 Information Security and Data Storage/Movement

Consent forms and other hard copy documents with identifying information (e.g. emergency contact page) will be filed in separate hanging folders from

any documents with study IDs and study data on them, so that the identifying information cannot be linked to the corresponding data.

Data from self-report measures will be collected through REDCap. The administering researcher will open the REDCap database from the study folder on a VA computer, and then ask the participants the questionnaires over the phone and record their answers directly into REDCap. Each set of questionnaires will be linked to subjects through their study IDs or other unique identifiers (no PII recorded in REDCap), and these identifiers will be recorded and tracked by the study team. When needed, a report or query of these outcome/response data from these questionnaires will be generated from REDCap and saved to the study folder.

Data pertaining to medication usage and other treatment received during the subject's study enrollment period will be gathered from VINCI and saved to the study folder. This data will be linked to participants by Study ID only.

